14.0 REGULATORY CONSIDERATIONS

This research study is sponsored by the Principal Investigator, [name], in collaboration with Brown University Oncology Research Group (BrUOG), which will serve as the central coordinating office for the study. This study is supported by Bayer (the makers of Xofigo ®).

14.1 Protection of Human Subjects

The Investigator must ensure that patients or their legally acceptable representatives are clearly and fully informed about the purpose, potential risks and other critical issues regarding clinical trials in which they volunteer to participate. Preparation of the consent form is the responsibility of the Investigator and must include all elements required by CFR 21 Part 50.25 and the local IRB.

14.2 Compliance with the Protocol and Protocol Revisions:

The study must be conducted as described in this approved protocol.

All revisions to the protocol must be provided to Brown University Oncology Research Group, and Bayer. The Investigator should not implement any deviation or change to the protocol without prior review and documented approval/favorable opinion from the IRB/IEC and Bayer of an Amendment, except where necessary to eliminate an immediate hazard(s) to study patients.

Documentation of approval signed by the chairperson or designee of the IRB(s)/IEC(s) must be sent to Brown University Oncology Research Group, and Bayer. If the revision is an Administrative Letter, Investigators must inform their IRB(s)/IEC(s).

The Investigator must ensure that patients or their legally acceptable representatives are clearly and fully informed about the purpose, potential risks and other critical issues regarding clinical trials in which they volunteer to participate. Preparation of the consent form is the responsibility of the Investigator and must include all elements required by CFR 21 Part 50.25 and the local IRB.

After the study has been fully explained, written informed consent will be obtained from either the patient or his/her guardian or legal representative prior to study participation. The method of obtaining and documenting the informed consent and the contents of the consent will comply with ICH-GCP and all applicable regulatory requirement(s).

14.3 Protocol amendments or changes in study conduct:

Any change or addition (excluding administrative) to this protocol requires a written protocol amendment that must be reviewed and approved by Brown University Oncology Research Group, Bayer and the investigator before implementation. Amendments significantly affecting the safety of subjects, the scope of the investigation or the scientific quality of the study require additional approval by the IRB at each study center. A copy of the written approval of the IRB must be provided to Brown University Oncology Research Group, and Bayer.

- Examples of amendments requiring such approval
- Increases in drug dose or duration of exposure of subjects
- Significant changes in the study design (e.g. addition or deletion of a control group)
- Increases in the number of invasive procedures
- Addition or deletions of a test procedure required for monitoring of safety.

These requirements for approval should in no way prevent any immediate action from being taken by the investigator or by Brown University Oncology Research Group and Bayer in the interests of preserving the safety of all patients included in the trial. If an immediate change to the protocol is felt to be necessary by the investigator and is implemented for safety reasons Brown University Oncology Research Group and Bayer must be notified and the IRB at the center must be informed immediately. Amendments affecting only administrative aspects of the study do not require formal protocol amendments or IRB approval but the IRB must be kept informed of such administrative changes.

Examples of administrative changes not requiring formal protocol amendments and IRB approval include:

- Changes in the staff used to monitor trials (Bayer considers a change in Principal Investigator or the addition of sub-site(s) to be substantial and requires Bayer approval prior to implementation)
- Minor changes in the packaging or labeling of study drug.

15.0 DATA MONITORING / QUALITY ASSURANCE/ RECORD RETENTION

15.1 Good Clinical Practice: The study will be conducted in accordance with the International Conference on Harmonisation (ICH) for Good Clinical Practice (GCP) and in the US Code of Federal Regulations. The investigator will be thoroughly familiar with the appropriate use of the drug as described in the protocol and Investigator's Brochure. Essential clinical documents will be maintained to demonstrate the validity of the study and the integrity of the data collected. Master files should be established at the beginning of the study, maintained for the duration of the study and retained according to the appropriate regulations.

15.2 Patient Confidentiality: In order to maintain patient privacy, all data capture records, drug accountability records, study reports and communications will identify the patient by initials and the assigned patient number. The investigator will grant monitor(s) and auditor(s) from Bayer or its designees and regulatory authority (ies) access to the patient's original medical records for verification of data gathered on the data capture records and to audit the data collection process. The patient's confidentiality will be maintained and will not be made publicly available to the extent permitted by the applicable laws and regulations.

15.3 Protocol Compliance: The investigator will conduct the study in compliance with the protocol given approval/favorable opinion by the IRB/IEC and the appropriate regulatory authority(ies). Changes to the protocol will require approval from Bayer and written IRB/IEC approval/favorable opinion prior to implementation, except when the modification is needed to eliminate an immediate hazard(s) to patients. The IRB/IEC may provide, if applicable regulatory authority (ies) permit, expedited review and approval/favorable opinion for minor change(s) in ongoing studies that have the approval /favorable opinion of the IRB/IEC. The investigator will submit all protocol modifications to Bayer and the regulatory authority (ies) in accordance with the governing regulations.

Any departures from the protocol must be fully documented in the source documents.

15.4 On-site Audits: Regulatory authorities, the IEC/IRB and/or Bayer clinical quality assurance group may request access to all source documents, data capture records, and other study documentation for on-site audit or inspection. Direct access to these documents must be guaranteed by the investigator, who must provide support at all times for these activities.

15.5 Drug Accountability: Accountability for the drug at all study sites is the responsibility of the principal investigator. The investigator will ensure that the drug is used only in accordance with this protocol. Drug accountability records indicating the drug's delivery date to the site (if applicable), inventory at the site (if applicable), use by each patient, and return to Bayer for disposal of the drug (if applicable and if approved by Bayer) will be maintained by the clinical site. Accountability records will include dates, quantities, lot numbers, expiration dates (if applicable), and patient numbers.

All material containing Xofigo ® will be treated and disposed of as hazardous waste in accordance with governing regulations.

15.6 Premature Closure of the Study: This study may be prematurely terminated, if in the opinion of the investigator or Bayer, there is sufficient reasonable cause. Written notification documenting the reason for study termination will be provided to the investigator or Bayer by the terminating party.

Circumstances that may warrant termination include, but are not limited to:

- Determination of unexpected, significant, or unacceptable risk to patients
- Failure to enter patients at an acceptable rate
- Insufficient adherence to protocol requirements
- Insufficient complete and/or evaluable data
- Plans to modify, suspend or discontinue the development of the drug
- Should the study be closed prematurely, all study materials must be returned to Bayer.

15.7 Record Retention:

The investigator will maintain all study records according to ICH-GCP and applicable regulatory requirement(s).

The Brown University Oncology Research Group, as coordinator of this study, is responsible for ensuring proper conduct of the study with regard to protocol adherence and the validity of the data recorded on the case report forms. The Principle Investigator ([name].) and Brown University Oncology Research Group Manager of Operations ([name]) will monitor this study. The case report forms will be monitored against the submitted documents every 3 months for accuracy, completeness, adherence to the protocol and regulatory compliance.

U.S. FDA regulations (21CFR312.62[c]) require all records and documents pertaining to the conduct of this study and the distribution of investigational drug, including CRFs, consents forms, laboratory test results and medication inventory records, must be retained by the Principal Investigator for 2 years after marketing application approval. If no application is filed, these records must be kept 2 years after the investigation is discontinued and the FDA and the applicable local health authorities are notified. Bayer will notify the Principle Investigator if an application is filed.

16.0 DATA SAFETY AND MONITORING BOARDS

All trials initiated by the Brown University Oncology Research Group (BrUOG) are subject to oversight by the Data Safety Monitoring Board (DSMB). This board meets two times per year with any additional meetings scheduled when needed. The responsibilities are as follows:

- Familiarize themselves with the research protocol (s)
- The DSMB reviews trial performance information such as accrual information.
- Review interim analyses of outcome data and cumulative toxicity data summaries to determine whether the trial should continue as originally designed, should be changed, or should be terminated based on these data.
- The DSMB also determines whether and to whom outcome results should be released prior to the reporting of study results.
- All adverse events are reviewed by the committee, with assurances that these have been in fact sent for review to all pertinent IRBs.
- Review of reports of related studies to determine whether the monitored study needs to be changed or terminated.
- Review major proposed modifications to the study prior to their implementation (e.g., termination, dropping an arm based on toxicity results or other reported trial outcomes, increasing target sample size).
- Following each DSMB meeting, provide the study leadership with written information concerning findings for the trial as a whole related to cumulative toxicities observed and any relevant recommendations related to continuing, changing, or terminating the trial.

The study leadership will provide information on cumulative toxicities and relevant recommendations to the local principal investigators to be shared with their IRB's.

17.0 STATISTICS

This protocol will evaluate the effect of Ra 223 on patients with NSCLC who had stable to responding disease after completion of first line chemotherapy. The primary end point is the proportion of patients who experience their first symptomatic skeletal event (including pathologic bone fracture, spinal cord compression, need for surgical intervention for a bone metastasis, and time to external beam radiotherapy) during study treatment. A second primary endpoint is to evaluate the reduction of SSEs after 4 cycles of treatment (approximately 4 months) following the first Ra 223. The control is a historic experimental arm consisting of 257 patients (the majority having advanced NSCLC) from a study by Rosen *et al*^{7,8} who received zoledronic acid 4mg q 3 weeks with concomitant antineoplastic therapy. Approximately 40% patients experienced their first symptomatic skeletal event by 4 months in that study.

We hypothesize that the addition of Ra 233 to standard chemotherapy would reduce the proportion of patients with first symptomatic skeletal event at 4 months by half, i.e., to 20% compared to historic controls who received zoledronic acid. Using Fisher's exact test, we calculated a sample size of 36 patients to detect this 20% difference in the proportion of patients

having their first symptomatic skeletal event at 4 months with power of 75% and two sided α error probability of 0.1.

Progression-free survival (PFS) and overall survival (OS): PFS and OS will be determined from the time of study entry.

Time to symptomatic skeletal events: Will be determined from the time of study entry.

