4.1 Duration of Treatment

Xofigo will be administered every 4 weeks for a maximum of 6 treatments. See 5.2 for reasons for study discontinuation. (Treatment should be administered within +/- 3 days). Treatment delays of up to 14 days due to patient, physician or facility scheduling issues should be reported but will not constitute a deviation.

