5.2 Dose Modification/Study Discontinuation

Toxicity: NCI common toxicity version 4 will be utilized to assess toxicity.

Every effort should be made to administer the full dosing regimen of Radium Ra 223 dichloride. Adjustment of dose level is not permitted.

- Blood transfusion at baseline is acceptable to obtain baseline value of ≥ 9 and between study drug administrations, but not on the same day as Xofigo administration. Use of biologic myeloid growth factors such as G-CSF, is allowed in the management of acute toxicity.

Gastrointestinal events:

Diarrhea should be treated as per local institutional practices. The next cycle should not begin before diarrhea is recovered to CTCAE v4 Grade 2 or less.

Nausea or vomiting should be treated as per local practice. A further dose of study medication should not be given before nausea or vomiting is recovered to CTCAE v.4 Grade 2 or baseline levels.

Xofigo will be permanently discontinued for the following:

- Symptomatic Skeletal Event:
 - Pathologic fracture: Pathologic fractures are to be treated in a manner that attempts to maintain the best functional status and quality of life. Study treatment should be discontinued if the pathologic fractures are due to disease.
 - Spinal cord compression: If the patient experiences spinal cord compression during the treatment period, the patient should be treated for the event, and may not receive further study drug administration.
 - Radiation therapy to bone
 - Surgery to bone
- Patients with lung cancer progression requiring treatment with chemotherapy, radiation or surgery.
- Unacceptable toxicity (see section 5)
- **Surgical Intervention:** If surgery is required, and not due to disease progression, the patient may continue with study treatment, following a period of at least 4 weeks, if this is considered safe in the treating Investigator's opinion.
- **Non-pathological fractures:** For traumatic fractures in weight-bearing bones during treatment phase, the study drug administration should be discontinued.
- Incidental, asymptomatic new or worsening bone metastases will not require discontinuation of Xofigo.

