Patients will undergo a baseline radiographic assessment with either a CT scan or PET scan after completion of 1st-line treatment as per institutional standard of care. Patients meeting study eligibility may be entered on the study. Patients will have a physical monthly prior to each Xofigo treatment. Patients with new signs or symptoms suggesting bone metastases, or other sites of disease progression, will have additional radiographic assessment for evaluation as per institutional standards. The primary endpoint will be the assessment of how many patients develop an SSE during the study treatment and in particular during the first 4 cycles (approximately 4 months) on study. Following completion of all 6 treatments, patients will undergo restaging radiographic studies as per institutional standard of care.

6.2 Alkaline Phosphatase Assessment:

Alkaline phosphatase was found to be an important biomarker in the ALSYMPCA trial.¹⁶ Alkaline phosphatase levels will be assessed at study entry and prior to each dose of Xofigo. We will secondarily assess the following: 1. Time to an increase in alkaline phosphatase by $\geq 25\%$ from baseline, 2. Alkaline phosphatase response (reduction of $\geq 30\%$ from baseline value), and 3. Normalization of the alkaline phosphatase level (defined as a return to normal range in patients with an elevated level at baseline).

6.3 Quality of Life Assessments:

The EORTC QLQ-C30 and BM22 questionnaires will be performed monthly prior to each administration of Xofigo, and at study completion. The EORTC QLQ-30 assesses quality of life in patients with cancer, and the BM22 assesses quality of life in patients with bone metastases.¹⁷

7.0 DEFINITION OF PROGRESSION:

Progression

- 7.1 Progression of bone metastases Symptomatic Skeletal Event:
 - Pathologic fracture: Pathologic fractures are to be treated in a manner that attempts to maintain the best functional status and quality of life. Study treatment should be discontinued if the pathologic fractures are due to disease.
 - Spinal cord compression: If the patient experiences spinal cord compression during the treatment period, the patient should be treated for the event, and may not receive further study drug administration.
 - Radiation therapy to bone
 - Surgery to bone
- Incidental, asymptomatic new or worsening bone metastases will not require discontinuation of Xofigo.

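### The first-named primary endpoint counts SSEs during up to 6 cycles of treatment, but the 40% benchmark, 20% target, test and sample size fit only the 4-month endpoint, and the plan does not say which is tested or whether SSEs after stopping Xofigo count

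*Protocol*

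**What the plan says.** Section 17.0, repeated in SAP 17.0, names two primary endpoints. The first is the proportion of patients with a first SSE; its list of qualifying events ends "need for surgical intervention for a bone metastasis, and time to external beam radiotherapy) during study treatment". The other is introduced separately: "A second primary endpoint is to evaluate the reduction of SSEs after 4 cycles of treatment (approximately 4 months) following the first Ra 223". Section 6.1 puts both windows in one sentence, asking "how many patients develop an SSE during the study treatment and in particular during the first 4 cycles".

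The design figures use one time point only. For the historical control of 257 patients: "Approximately 40% patients experienced their first symptomatic skeletal event by 4 months in that study". The target is 20% at 4 months, and the 36 patients are justified by the proportion "having their first symptomatic skeletal event at 4 months with power of 75"%, using Fisher's exact test at two-sided 0.1.

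On the length of treatment, Section 4.1 says "Xofigo will be administered every 4 weeks for a maximum of 6 treatments". Xofigo can stop earlier for reasons other than an SSE. Section 5.2 includes "Patients with lung cancer progression requiring treatment with chemotherapy, radiation or surgery", and Section 12.0 adds toxicity, refusal and others. Section 13.0 and footnote H of the study calendar keep collecting time to first SSE for up to 1 year after stopping. Neither says whether those later events enter a primary proportion.

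**The concern.** The trial has one arm and is judged against one historical percentage. That comparison is meaningful only if the trial's proportion is measured over the same window, and by the same counting rule, as the benchmark. The first-named endpoint has a patient-specific window: up to 6 cycles for some, one or two for others. It therefore does not estimate a 4-month risk, and the documents give no other benchmark for it.

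Two errors pull in opposite directions. A window longer than 4 months raises the count and makes 40% too strict a yardstick. Ignoring SSEs after early stopping lowers the count and makes 40% too lenient. With two endpoints called primary, no rule for choosing between them and an open counting rule at 4 months, the choice could be made after the data are seen.

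**Working it through.** **1. The plan's own figure.** Inputs from Section 17.0: 36 patients at 20%, 257 controls at 40%, two-sided Fisher test at 0.10. Exact enumeration gives power of 76.4% at n = 36 (76.3% at 35, 74.9% at 34). The stated 36 patients and 75% power are therefore sound for the 4-month comparison. With 103/257 control events, the largest favourable result is 9/36 (p = 0.0995); 10/36 gives p = 0.201.

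Below, *false-favourable* means a significantly lower rate than control when the drug is no better than control. For a complete 4-month count this is 3.7%. (The two-sided rejection rate under no effect is 7.9%.)

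**2. Windows side by side.**

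| Element | Window |
|---|---|
| First-named primary endpoint | On treatment, up to 6 cycles; end not defined |
| Second primary endpoint | 4 cycles, about 4 months from first dose |
| Benchmark 40%, target 20%, N = 36 | 4 months |

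**3. If the on-treatment count were read against 40%.** Assumptions, because the documents give none of these: constant, independent hazards; 0–50% stopping by 4 months for reasons other than an SSE; 40% is a complete 4-month risk; 4 months = 365.25/3 = 121.75 days. The end of treatment is undefined, so two dates are used: the end of cycle 6 (6 × 28 = day 168) and the sixth dose (5 × 28 = day 140). No dosing delays.

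λ = −ln(1 − p4)/121.75, where p4 is the complete 4-month SSE risk; μ = −ln(1 − stop)/121.75; on-treatment proportion by day T = λ/(λ+μ) × (1 − exp(−(λ+μ)T)).

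Example with no effect, 20% stopping, T = 168: λ = 0.004196, μ = 0.001833, so 0.6960 × (1 − exp(−1.0128)) = 0.6960 × 0.6368 = 44.3%.

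P(favourable) is the sum over c ~ Bin(257, 0.40) of P(X ≤ b(c)), with X ~ Bin(36, p). Here b(c) is the largest favourable count with Fisher p ≤ 0.10.

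| Stopping by 4 months | 0% | 20% | 30% | 40% | 50% |
|---|---|---|---|---|---|
| Day 168: proportion, no effect | 51% | 44% | 41% | 38% | 34% |
| Day 168: false-favourable | 0.1% | 1.2% | 2.8% | 6.3% | 12.9% |
| Day 168: power if 20% is true | 43% | 62% | 71% | 79% | 86% |
| Day 140: proportion, no effect | 44% | 40% | 37% | 35% | 32% |
| Day 140: false-favourable | 1.1% | 4.1% | 7.3% | 12.4% | 20.5% |
| Day 140: power if 20% is true | 64% | 76% | 82% | 87% | 91% |

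**4. If the 4-month endpoint were counted only on treatment** (same formula, T = 121.75). At 20/30/40/50% stopping, a drug with no effect shows 36/34/32/30%. The false-favourable chance is 9/13.5/20/28.5%, against 3.7% for a complete count.

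**5. If the control's 40% was itself an on-study count.** Solve λ so that the on-treatment 4-month proportion is 40% at 20/30/40/50% stopping. A drug no better than control then shows 49/47/46/45% on the day-168 count and 44/47/50/53% on a complete 4-month count. The bias now runs against the drug.

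**6. Deaths and losses under a complete 4-month count.** If half of a 30% stopping hazard is death without SSE, counted as no event (replace μ by μ/2, T = 121.75), no effect shows 36.9%, with 7.7% false-favourable and 83% power. Counting death as an event gives 49.8%. Counting 1 or 2 lost patients as no event raises the false-favourable chance to 4.8% or 6.1%. Counting them as events lowers power to 66% or 55%.

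**The case against.** The strongest reply is that the tested comparison can be identified: benchmark, target, test and sample size are all tied to 4 months, and Section 6.1 stresses the first 4 cycles. This stands as an inference, and it limits the severity. What is missing is an explicit statement, and the text calls that endpoint the second one.

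Read literally, the first endpoint's wording already excludes SSEs after stopping. That also stands. The remaining gaps are when study treatment ends and the silence of the 4-month endpoint.

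Three stronger readings are tempting, and the documents support none of them:

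- *The sample size is wrong.* It reproduces for the 4-month comparison.
- *The plan tests the on-treatment count against 40%, or accepts success on either endpoint.* No such test or rule is written, so step 3 shows only what would follow if someone did so.
- *The design favours the drug.* The direction depends on stopping, on the end-of-treatment date and on how the control was counted. With 20% stopping and treatment ending at day 140, the on-treatment count behaves almost like the complete 4-month count (4.1% and 76.1%).

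The stopping rates and the independence assumption are mine. Stopping for progression may well be related to SSE risk. Permitted delays (Sections 4.1 and 5.1) would lengthen the windows.

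**Conclusion.** The point holds as a gap in specification that should be fixed; it does not invalidate the design. The first-named primary endpoint has no matching comparator, target or power. The endpoint that does match is labelled second and has no counting rule for SSEs after Xofigo stops, and nothing says how two primary endpoints are to be handled.

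This rests on the text and is secure. The sizes in steps 3 and 4 are conditional. They assume constant independent hazards, 0–50% stopping and a control rate that is a complete 4-month risk. They show that the choice of window and counting rule can change the trial's operating characteristics materially. They do not establish which way a bias would run.

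**What to change.** In Sections 6.1 and 17.0 and SAP 17.0:

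- Name one tested primary endpoint: first SSE within 4 months of the first Xofigo dose, in all patients given at least one dose. State the number of days once: 4 cycles are 112 days and 4 calendar months about 122. Under the assumptions of step 3, a complete 112-day count shows 37.5% with no effect (6.7% false-favourable).
- Count SSEs whether or not Xofigo has stopped, using the follow-up already in Section 13.0.
- Make the on-treatment proportion descriptive, and define when study treatment ends for that purpose.
- Add a sensitivity analysis for death without SSE (as a competing event, or counted as an event), and state how patients lost before the cut-off are counted.
- State that N = 36 and about 76% power hold when deaths and losses before 4 months are few.
- State beside the 40% how the control counted patients who stopped or died.

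The cost is wording; no visits are added. The downside is that the reported proportion will be somewhat less favourable than an on-treatment 4-month count.

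Two minor alignments can be made at the same time. Section 12.0 item 9 omits SSE follow-up after refusal of treatment, although Section 13.0 includes it. The time-to-SSE analysis starts at study entry ("Time to symptomatic skeletal events: Will be determined from the time of study entry"), whereas the 4-month endpoint starts at the first dose.
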